- **Preliminary study 2.** We have recently demonstrated the utility of the proposed experimental paradigm (i.e. EVO) and the proposed processing speed outcome measure in people with MS. Specifically, in a behavioral intervention study, MS patients who played EVO improved information processing speed ( $p=0.003$ ) ([name] et al., 2019). In a follow-up randomized controlled pilot trial, the mean increase in SDMT was 6.10 for EVO task group compared with 3.55 for an active control group, with clinically improvement significantly more likely to be retained for at least two months in the EVO group ([name] et al., 2019). *These preliminary results provide additional support for the feasibility of using the proposed experimental paradigm in MS and the selection of outcome measures for Specific Aim 1.* In this preliminary study, we also demonstrated that SDMT improvement was found to be associated with clinical severity, which revealed that clinical data contributes to the change of SDMT scores. This shows that, *given the heterogeneity of MS, understanding individual variability is critical for clinical trials assessing cognitive function interventions in MS, and underscores the importance of Specific Aim 2* ([name] et al., 2019).

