## Statistical Design and Power

**Power.** Twenty participants in a group will correspond with  $>80\%$  power ( $1-\beta$ ) at a 95% significance level ( $1-\alpha$ ) as calculated from our preliminary studies (detailed below).

**Primary outcome measure: Divided attention.** Results from Preliminary Study 1 showed that Verum (6 Hz) tACS, and not control tACS, yielded improved divided attention discrimination performance in healthy adults, as indexed by d-prime ( $F(1,35) = 6.63$ ,  $p = 0.01$ ,  $\eta_p^2 = 0.16$ ). Here, it is hypothesized that MS patients who receive Verum tACS will exhibit comparable performance gains in divided attention. To test this, a divided attention index will be calculated from performance during the discrimination task as the cost in d-prime (i.e., d-prime dual task minus d-prime single task). Data will be submitted to an ANCOVA with Group (Verum, Control) and Session (pre-tACS, post-tACS) as factors. Although age will be matched across groups, age will serve as the covariate to account for within-group differences. A Group x Session interaction is expected to show that the Verum tACS group, compared to the control group, will exhibit a larger reduction in d-prime cost post-tACS, indicating enhanced divided attention ability. For this interaction, 20 participants per group will yield  $>95\%$  power ( $1-\beta$ ) at a 95% significance level ( $1-\alpha$ ) with an expected effect size of  $f = 0.28$ .

**Primary outcome measure: Processing speed.** Results from Preliminary Study 2 showed that cognitive training with EVO improves processing speed, as indexed by the SDMT score ( $t(17) = 3.19$ ,  $p = 0.005$ ,  $d = 0.34$ ). Here, it is hypothesized that MS patients who receive Verum tACS will exhibit comparable performance gains in processing speed. To test this, SDMT score will be submitted to an ANCOVA with Group (Verum, Control) and Session (pre-tACS, post-tACS) as factors. Although age will be matched across groups, age will serve as the covariate to account for within-group differences. A Group x Session interaction is expected to show that the Verum tACS group, compared to the control group, will exhibit a higher SDMT score post-tACS, indicating enhanced processing speed. For this interaction, 20 participants per group will yield 80% power ( $1-\beta$ ) at a 95% significance level ( $1-\alpha$ ) with an expected effect size of  $f = 0.19$ .

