**Secondary outcome measure: Frontal theta power.** Results from Preliminary Study 1 also showed that the Verum tACS group, and not control tACS, exhibited a correlation between divided attention and frontal theta power such that those participants with the greatest increase in frontal theta power yielded the greatest improvement in divided attention ability ( $r = 0.50$ ,  $p = 0.04$ ). Here, it is hypothesized that MS patients who receive Verum tACS will exhibit similar neuroplastic changes in frontal theta activity. To test this, frontal theta power will be extracted during the discrimination task (theta dual task minus theta single task) and a change score will be calculated (post-tACS minus pre-tACS). A regression analysis will be conducted between theta power and the change in the divided attention index (post-tACS minus pre-tACS) described above. It is expected that increases in theta power only the Verum tACS group will be related to improvements in divided attention ability. To further characterize between group differences, theta power will be submitted to an ANCOVA with Group (Verum, Control) and Session (pre-tACS, post-tACS) as factors. Although age will be matched across groups, age will serve as the covariate to account for within-group differences. A Group x Session interaction is expected to show that the Verum tACS group, compared to the control group, will exhibit a larger increase in theta power post-tACS, indicating enhanced neuroplasticity. For this interaction, 20 participants per group will yield  $>95\%$  power ( $1-\beta$ ) at a 95% significance level ( $1-\alpha$ ) with an expected effect size of  $f = 0.28$ .

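### The Group x Session analyses name age as covariate without saying that it acts on change, and the SDMT test omits clinical severity, which the pilot links to SDMT change: a cheap improvement

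*Combined protocol and SAP*

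**What the plan says.** All references are to the combined protocol and SAP.

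- **Model.** In Statistical Design and Power, both primary outcomes (d-prime cost and SDMT) go into an "ANCOVA with Group (Verum, Control) and Session (pre-tACS, post-tACS) as factors". The theta-power paragraph repeats this: "theta power will be submitted to an ANCOVA with Group (Verum, Control) and Session (pre-tACS, post-tACS) as factors".
- **Covariate.** In all three places age is the only one: "Although age will be matched across groups, age will serve as the covariate to account for within-group differences". Study Design also says that the groups are age-matched.
- **Tested effect.** It is the Group x Session interaction. The Verum group is expected to show more benefit: for divided attention it "will exhibit a larger reduction in d-prime cost post-tACS, indicating enhanced divided attention ability", and for processing speed it "will exhibit a higher SDMT score post-tACS, indicating enhanced processing speed".
- **What is not given.** No model equation, error structure or software is stated. An Age x Session term is neither written nor ruled out.
- **Severity.** Preliminary study 2 reports that "SDMT improvement was found to be associated with clinical severity, which revealed that clinical data contributes to the change of SDMT scores". It names no severity measure and gives no strength. In the covariates item under Outcome measures, MSFC4 is the severity metric for the Aim 2 regression. EDSS is listed there with the usual clinical features and is also an entry criterion. Neither is in the Aim 1 models.

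**The concern.** With two sessions and complete data, Group x Session is the between-group difference in mean change. Age is fixed within a participant. A main effect of age moves both sessions by the same amount and drops out of the difference. On that reading, the only adjustment in the primary analysis does nothing for the hypothesis being tested. If age matching works and age does predict change, the error term is then larger than it need be.

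An analyst whose software adds Age x Session would obtain a different estimate, standard error and error df (37, not 38) from the same sentence of the plan. A primary analysis should not depend on a software default.

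Severity raises a related question for SDMT. The pilot ties it to the very quantity compared between arms. Entry is broad (relapsing or progressive MS, EDSS up to 6.5), and age is the only factor stated to be matched. With 20 per arm, a chance difference in severity would go unadjusted.

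**Working it through.** **1. The plan's own power figures.** Inputs from Statistical Design and Power: 20 per group (N = 40), m = 2 sessions, alpha 0.05, f = 0.19 with 80% power for SDMT, and f = 0.28 with more than 95% for divided attention. The pre-post correlation rho is not stated. Formula: lambda = f² x N x m / (1 - rho), noncentral F with df 1, 38.

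- rho = 0.50: 0.19² x 80 / 0.50 = 5.78, power 64.9%. For f = 0.28, 0.28² x 80 / 0.50 = 12.54, power 93.2%.
- rho = 0.65: 0.19² x 80 / 0.35 = 8.25, power about 80%. For f = 0.28, 0.28² x 80 / 0.35 = 17.92, power 98.5%.

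An unstated rho of about 0.65 fits both figures, so they are neither confirmed nor shown wrong. The stated 80% for SDMT is taken as the starting point below.

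**2. What an age main effect does.** For participant i at session s, write Y = a + b·Group + c·Session + d·Group x Session + e·Age + u_i + error. Then post minus pre = c + d·Group + (difference of errors). The term e·Age has gone. With Age x Session added (coefficient g), post minus pre = c + d·Group + g·Age + error, and age acts on d.

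Three simulated complete data sets (20 per arm, assumed age slope on change) give these Group x Session estimates (SE):

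| Data set | No age | Age main effect | Age x Session added |
|---|---|---|---|
| 1 | 0.297 (0.252) | 0.297 (0.252) | 0.430 (0.198) |
| 2 | 0.608 (0.237) | 0.608 (0.237) | 0.591 (0.241) |
| 3 | 0.189 (0.242) | 0.189 (0.242) | 0.225 (0.246) |

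The first two model columns are identical. The third matches a regression of change on Group and age. These runs show the identity, not the likely gain; in two of the three the SE rose slightly. With 4 of 40 post scores missing in a mixed model, an age main effect moved the estimate a little (0.958 to 0.969), so exact equality needs complete data.

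**3. Size of the possible gain for SDMT.** 80% power with df 1, 38 corresponds to lambda = 8.265. A covariate with correlation r with change multiplies lambda by 1 / (1 - r²) and leaves df 1, 37. The confidence interval narrows by about 1 - sqrt(1 - r²). All r are assumptions.

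| r | lambda | Power | CI narrower by |
|---|---|---|---|
| 0 | 8.265 | 79.9% | 0% |
| 0.2 | 8.610 | 81.5% | 2% |
| 0.3 | 9.083 | 83.5% | 5% |
| 0.4 | 9.839 | 86.3% | 8% |
| 0.5 | 11.020 | 89.8% | 13% |

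A gain of 5 points needs r of about 0.36. Two covariates that are both unrelated to change (lambda 8.265, df 1, 36) still give 79.9%.

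**4. Chance imbalance in severity.** Without stratification, the difference in mean severity between arms has SE sqrt(2/20) = 0.32 SD. At r = 0.3, a 2-SE imbalance shifts the SDMT contrast by 2 x 0.3 x 0.316 = 0.19 SD of change. An imbalance that large in either direction arises in roughly 1 trial in 20.

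**The case against.** **The model text may be shorthand.** The factor list does not spell out Group x Session as a term either; it appears only as the expected finding. A standard repeated-measures GLM fits a between-subject covariate at every session and so carries Age x Session. This stands. A reader might infer that age cannot affect the tested effect, but the documents do not support that, because they fix no model form. What they support is that the model is under-specified and that one natural reading makes the adjustment inert.

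**Severity is not forgotten.** It is an Aim 2 predictor of tACS effects on both primary outcomes, and Preliminary study 2 itself points to Aim 2. This also stands. The Aim 2 regression does not adjust the Aim 1 comparison, however. A reader might infer that the omission biases the primary test; under randomisation it does not.

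**The pilot supports less than it may seem to.** It names no severity measure, and the association concerns SDMT, so it gives no ground for adding severity to the divided-attention or theta models. It does not single out EDSS.

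**The gain is conjectural.** No correlation of age or severity with change is reported. At r of 0.2 to 0.3 the gain is 1.5 to 3.5 points of power. That is modest, which is why this is an inexpensive improvement and not a defect that threatens the trial.

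**Conclusion.** The point holds as a cheap improvement. If age enters as a main effect only and the data are complete, it leaves the Group x Session estimate and SE exactly unchanged for both primary outcomes and for theta power. Whether that is the intended model cannot be settled from the text. For SDMT, leaving severity out of the Aim 1 model gives up precision and leaves chance imbalance unadjusted, but causes no bias.

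The size rests on an assumed r. From the stated 80%, power ranges from 79.9% at r = 0 to 89.8% at r = 0.5. The algebra does not depend on the power figures. The power table takes the stated 80% as given, and that in turn needs a pre-post correlation of about 0.65, which the plan does not report.

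**What to change.** In Statistical Design and Power, write out the model for d-prime cost, SDMT and theta power in one of these forms:

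1. Repeated measures with Group, Session, Group x Session, Age and Age x Session.
2. Change (session 5 minus session 1) regressed on Group and age. With complete data this is the same test as form 1.
3. The session 5 score regressed on the session 1 score, Group and age. The session 1 score must be in the model. Without it, the analysis uses the post score alone. At a pre-post correlation of 0.65, change has 2 x (1 - 0.65) = 0.70 of the post-score variance, so lambda falls to 8.265 x 0.70 = 5.79. SDMT power then drops from 80% to about 65% (df 1, 37, ignoring any gain from age).

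For the SDMT model only, pre-specify one baseline severity measure that is already collected, entered so that it acts on change (interacting with Session in form 1); as a main effect only it would be as inert as age. EDSS is one candidate. MSFC4 is the other: the plan names it as its severity metric, but it contains PASAT, a processing-speed test, so its overlap with baseline SDMT needs thought. Choose one before unblinding.

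The cost is wording and one error degree of freedom per covariate (38 to 37, or 36 with both). No new data are needed.

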## Study Design

**Overall strategy.** We will enroll forty adult MS patients (aged 18-65 years) randomly assigned to one of two groups: either a Verum (6 Hz) tACS group or a Frequency Control (1 Hz) group. Twenty participants in each group will correspond with >80% power ( $1-\beta$ ) at a 95% significance level ( $1-\alpha$ ) as calculated from our preliminary studies. The two groups will be age-matched. A randomized double-blinded, placebo controlled, multi-session

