## Preliminary Studies

- **Preliminary study 1.** We have previously demonstrated (and replicated) that theta-tACS above PFC is able to enhance divided attention abilities in healthy young adults with a large effect size ( $d = 0.96$ ) ([name] et al., 2019; [name] et al., 2017). More recently, we replicated these effects again in healthy older adults (aged 60 – 80 years) and further demonstrated that this improvement in attention sustains for at least a month following the last tACS treatment (manuscript in preparation). Moreover, the improvements in divided attention were correlated with increases in PFC theta activity. Although we did not assess processing speed, we did observe changes in response times during the divided attention task, suggesting processing speed may have contributed to (or co-occurred with) the improvements in divided attention. *These studies support the notion that the proposed tACS approach is a promising for treatment for cognitive decline in MS – specifically divided attention and processing speed (Specific Aim 1).* In this preliminary study, we also observed tACS effects were positively correlated with the magnitude of the individual MRI-based modeled electric field in the brain. *This provides support for our hypothesis that anatomical factors affect tACS outcomes (Specific Aim 2).*

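### Divided attention: the cited preliminary result gives about 74% power at 20 per group, not >95%; the >95% for theta has no cited Group x Session effect behind it

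*Combined protocol and SAP*

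**What the plan says.** Under Statistical Design and Power, the general statement is more than 80% power with 20 per group, "as calculated from our preliminary studies (detailed below". Study Design makes the same claim, "as calculated from our preliminary studies".

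- **Divided attention (primary).** Preliminary Study 1 is cited as showing that "Verum (6 Hz) tACS, and not control tACS, yielded improved divided attention discrimination performance in healthy adults, as indexed by d-prime", with F(1,35) = 6.63, p = 0.01 and partial eta-squared 0.16. The plan hypothesises that "MS patients who receive Verum tACS will exhibit comparable performance gains in divided attention". The planned test is the Group x Session interaction on d-prime cost, with age as covariate. The power statement is "indicating enhanced divided attention ability. For this interaction, 20 participants per group will yield $>95\%$ power", at an expected f of 0.28.
- **Processing speed (primary).** "indicating enhanced processing speed. For this interaction, 20 participants per group will yield 80% power", at f = 0.19.
- **Frontal theta (secondary).** "indicating enhanced neuroplasticity. For this interaction, 20 participants per group will yield $>95\%$ power", again at f = 0.28. The theta result cited there is a correlation within the Verum group, r = 0.50, p = 0.04.

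Preliminary Studies also reports that theta-tACS can "enhance divided attention abilities in healthy young adults with a large effect size", d = 0.96, without saying what contrast or standardiser d refers to. Neither a conversion from partial eta-squared 0.16 to f = 0.28 nor a pre-post correlation is given.

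**The concern.** The preliminary F came from about the same number of people as the trial will enrol. With 1 and 35 degrees of freedom and two groups, that is 37 people against 40. A result with p of about 0.014 in 37 people cannot, taken at face value, predict more than 95% power in 40, because the expected test statistic is only slightly larger than the one observed, and the observed one was not far beyond the 5% threshold.

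The power statements, together with the processing-speed line, are all the plan offers to justify 20 per group. If the divided-attention figure is overstated, a null result on that outcome would be read as stronger evidence against an effect than the cited data allow.

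**Working it through.** **Inputs.** From Statistical Design and Power: N = 40 (20 per group), two-sided alpha 0.05, f = 0.28 and f = 0.19, F(1,35) = 6.63, partial eta-squared 0.16. From Preliminary Studies: d = 0.96. Assumptions: the F is the Group x Session interaction in a two-group study of 37, and the pre-post correlation (rho), which is not stated, is varied.

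**1. The cited result is internally consistent.** p = 0.0144; partial eta-squared = 6.63/(6.63 + 35) = 0.159. With groups of 18 and 19, the difference in change is sqrt(6.63) x sqrt(1/18 + 1/19) = 0.85 SD of change.

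**2. The plan's own figure.** In the usual repeated-measures convention for a two-group, two-session interaction, the noncentrality is lambda = f² x 40 x 2/(1 - rho), with 1 and 38 df. The implied partial eta-squared is lambda/(lambda + 38).

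| f | rho | lambda | Power | Implied partial eta-squared |
|---|---|---|---|---|
| 0.28 | 0 | 6.27 | 68.5% | 0.14 |
| 0.28 | 0.30 | 8.96 | 83.1% | 0.19 |
| 0.28 | 0.50 | 12.54 | 93.2% | 0.25 |
| 0.28 | 0.54 | 13.63 | 94.9% | 0.26 |
| 0.28 | 0.65 | 17.92 | 98.5% | 0.32 |
| 0.19 | 0.65 | 8.25 | 79.9% | 0.18 |

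So >95% is reproducible from f = 0.28 once rho is about 0.54 or higher. A rho of 0.65 reproduces the processing-speed line (80% at f = 0.19).

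**3. Power at the cited effect.** No value of rho is needed here, because the F already reflects the correlation in the preliminary data.

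| Scaling | lambda | df | Power |
|---|---|---|---|
| F x 40/37 | 7.17 | 38 | 74.2% |
| (0.16/0.84) x 38 | 7.24 | 38 | 74.6% |
| (0.16/0.84) x 40 | 7.62 | 38 | 76.7% |
| 38 people with one covariate, F x 40/38 | 6.98 | 37 | 73.0% |

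The lambda needed is 8.27 for 80% power and 13.69 for 95%. Since lambda = 10 x (difference in SD of change)² at 20 per group, these are sqrt(0.827) = 0.91 SD and sqrt(1.369) = 1.17 SD, against the cited 0.85 SD. The cited effect would need 23 per group for 80% and 38 per group for 95%.

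**4. Can f = 0.28 be the cited effect?** Setting 0.0784 x 80/(1 - rho) equal to 7.24 or 7.62 gives rho = 0.13 or 0.18. There, power at f = 0.28 is the same 75% or 77%. At rho = 0.65 the cited effect is f = sqrt(7.17 x 0.35/80) = 0.18, slightly below the 0.19 that the plan itself equates with 80% power.

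**5. Sensitivity.**
- d = 0.96, if it is a between-group change-score effect: lambda = 10 x 0.96² = 9.22, power 84%.
- Age covariate (37 df): it would have to explain about 13% of change-score variance to bring the cited effect to 80% power, and about 48% to bring it to 95%.
- Precision: the 95% interval for the noncentrality behind F = 6.63 is 0.22 to 21.2. Scaled by 40/37, that gives power from about 8% to over 99%.

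**6. Theta.** The correlation of r = 0.50 describes how theta change and attention change vary together among Verum patients. It carries no information on the difference in theta change between groups, so no Group x Session f can be derived from it.

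**The case against.** The strongest reply is that nothing has been miscalculated. At f = 0.28 and a rho of 0.55, power is 95.3%, and the plan calls f = 0.28 an expected effect size without saying it was converted from the cited F. The F is not labelled as the interaction, is described in terms of d-prime rather than d-prime cost, and cannot be tied to one of the several studies grouped as Preliminary Study 1. The rho of 0.65 is borrowed from a different outcome. With d = 0.96 power would be 84%, so the overall >80% is not refuted on every reading. The interval around 74% is also wide enough to include >95%.

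Much of this is right as description. The fault is not in the software step but in the step from evidence to f, and 74% is power at a point estimate from a small study in healthy adults. None of it rescues the stated figure. The plan says its power comes from the preliminary studies and gives this F as the detail. The 74% does not depend on rho. No cited effect reaches 95%: d = 0.96 stops at 84%. The plan gives no figure for how much variance age explains, and 48% would be needed. A wide interval is a reason against a flat >95%, not for it. The overall >80% could stand only if the plan named d = 0.96 as its basis and showed it to be a between-group change-score effect.

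**Conclusion.** The concern holds. On the result the plan cites for its first primary outcome, 20 per group gives about 74% power (73-77%), some 20 points below the stated >95% and short of the overall >80%. Either f = 0.28 represents the cited study and power is about 75%, or power exceeds 95% and the assumed effect (partial eta-squared at least 0.26, about 1.17 SD of change or more) is much larger than the one cited. This rests on reading F(1,35) as the two-group, two-session interaction and on a two-sided 5% test. The theta figure is unsupported by anything cited, which is a weaker finding than being wrong. It should be fixed, but it does not affect how the trial is run.

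**What to change.** 1. Preferably replace the divided-attention power with the detectable difference: 0.91 SD of change at 80% power, 20 per group, two-sided 0.05. Alternatively state about 74% at the cited partial eta-squared of 0.16, and say that this is a point estimate from a small study in healthy adults.
2. If f = 0.28 has another source, cite it.
3. State the effect-size convention and the assumed pre-post correlation for each interaction.
4. Bring the overall >80% statements in Study Design and in Statistical Design and Power into line.
5. For theta, remove the >95% or base it on a Group x Session theta effect.

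The cost is protocol wording and a less favourable stated power. No additional patients, visits or analyses are needed.

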**Fig 1. Structure of the experiments**

experiment is proposed to assess whether tACS may yield improvements in divided attention and information processing speed in MS (Specific Aim 1) and identify predictive factors of response to tACS (Specific Aim 2). The experimental paradigm consists of 5 daily sessions (conducted over up to 10 days) (Fig 1). During session 1 (baseline; pre-tACS) and session 5 (follow-up; post-tACS), participants will be assessed on divided attention while electroencephalography (EEG) data is acquired. EEG data will enable assessments of neuroplastic changes associated with tACS effects on divided attention and it will also serve to quantify cortical excitability as a predictor for tACS effects. Additionally, processing speed will be assessed along with questionnaires on pain and fatigue. During sessions 2-4, tACS will be applied while participants are engaged in a tablet-based multitasking task, which includes divided attention and processing speed components, but is distinct from the primary outcome measures.

**Inclusion/Exclusion Criteria.** Inclusion Criteria: age 18-65, diagnosis of MS (relapsing or progressive) according to McDonald criteria (Polman et al., 2011), Expanded Disability Status Scale (EDSS)≤6.5 (Noseworthy et al., 1990), no paresis of the upper limbs, a minimum of 3 months since the last relapse, no severe depression (Beck Depression Inventory<19), normal hearing, and no changes in MS or symptomatic medications in past 2 months. Exclusion Criteria: prior brain surgery, clips in brain, epilepsy or other neurological or non-affective psychiatric disorders, pregnancy.

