### **Interventions (Sessions 2 – 4).**

○ **Transcranial alternating current stimulation (tACS).** TACS will be applied at 6 Hz for the Verum tACS group and 1 Hz tACS for the Frequency Control group because higher frequencies of stimulation (above theta) may introduce visual flickering (or phosphenes) that could confound the interpretation of the data (Paulus, 2010; Schutter & Hortensius, 2010). Moreover, 1-Hz tACS has not been associated with cognitive alterations (Antal et al., 2008; Castillo Saavedra et al., 2014) and we have verified its use as a control in Preliminary Study 1. A sinusoidal alternating current of 1mA peak amplitude (2mA peak-to-peak amplitude) will be delivered via a pair of Ag/AgCl electrodes ( $3.14\text{ cm}^2$ ) through a Starstim-32 device (Neuroelectrics, Spain) while patients are engaged in a tablet-based cognitive task (EVO, see below). During each session, participants will receive 20 min of stimulation with a 15-s ramp up and 15-s ramp down. The stimulation electrodes will be located at F3 and F4 of the 10–20 electrode coordinate system (above PFC). Impedance will be kept below 10 kΩ. In order to confirm that the frequency control was an appropriately blinded manipulation and all patients tolerate tACS well, all patients will be asked to complete a 1-min survey to scale the perception of stimulation (headache, scalp pain, tingling, burning sensation) from 1 (mild) to 10 (severe) at the end of each session. If the score on the stimulation perception survey is below 4 for each item, tACS will be considered well-tolerated.

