○ **Cognitive paradigm.** During tACS, participants will be engaged in a divided attention paradigm known as EVO (Akili Labs, Boston) (Anguera et al., 2017; Anguera, Jordan, Castaneda, [name], & Arean, 2016; Arean et al., 2016; Davis, Bower, & Kollins, 2018). The EVO paradigm consists of a divided attention paradigm that combines visuomotor tracking and perceptual discrimination tasks similar to, but distinct from, those used for our outcome measure of divided attention. EVO utilizes adaptive algorithms to change game difficulty on a trial-by-trial basis for both the perceptual discrimination (adapting the response window for a target) and visuomotor tracking (adapting the speed of the forward path and sensitivity of the user's motions), with real-time feedback making the patients aware of their performance. More specifically, the adaptive algorithm makes proportional changes in gameplay difficulty when the participant's performance deviates from an 80% accuracy median, which ensures that task difficulty is equated across participants and enhances participant engagement so that the paradigm is never too easy (or boring) nor too difficult (or frustrating). Each task lasts approximately 4 minutes, with 7 task runs comprising one session (experimental day). As the

patients improve their performance throughout gameplay, they are transported to different visual “worlds” in the EVO universe, meant to immerse the participant and enhance the depth of engagement and compliance. Audio and visual cues are continuously available to the participant so they are given feedback as to their performance. Since the adaptive mechanics strive to keep the participant at ~80% accuracy, the participant is challenged to constantly improve upon their own cognitive control performance in order to reach the next level.

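### The 80% SDMT power does not follow from the EVO training gain cited for it, and the documents give no 6 Hz versus 1 Hz estimate for SDMT

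*Combined protocol and SAP*

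**What the plan says.** Study Design, under overall strategy, makes a trial-level claim: "Twenty participants in each group will correspond with >80% power". Statistical Design and Power repeats it and gives the basis: "as calculated from our preliminary studies (detailed below").

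For processing speed, that section starts from the second preliminary study: "Results from Preliminary Study 2 showed that cognitive training with EVO improves processing speed, as indexed by the SDMT score", with t(17) = 3.19, p = 0.005, d = 0.34. It continues: "it is hypothesized that MS patients who receive Verum tACS will exhibit comparable performance gains in processing speed". The test is the Group x Session interaction in an ANCOVA with age as covariate. For that interaction, "20 participants per group will yield 80% power", with an expected effect size of f = 0.19. The plan does not say how f was obtained or what correlation between the two sessions was assumed.

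On what the arms receive, the text around Fig 1 says: "During sessions 2-4, tACS will be applied while participants are engaged in a tablet-based multitasking task". The Interventions section names that task as EVO and makes no distinction between arms: "During tACS, participants will be engaged in a divided attention paradigm known as EVO". The arms differ in stimulation frequency, 6 Hz or 1 Hz.

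**The concern.** The interaction tests whether SDMT changes more under 6 Hz than under 1 Hz stimulation. The cited result is a gain with EVO training, which both arms receive. If EVO produced the same gain in both arms, the expected interaction would be zero however large that gain was.

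Nothing else in the documents supplies the missing estimate. Preliminary Studies says the tACS study did not measure processing speed and offers response-time changes only as suggestive. Its randomised pilot compares EVO with an active control (mean SDMT increases of 6.10 and 3.55, without SDs), which is a different contrast. The rationale in the Interventions section cites tACS for divided attention and EVO alone for processing speed.

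If the SDMT result is null, a reader will take the trial to have had 80% power grounded in data. The plan does not say what 6 Hz versus 1 Hz difference it could detect.

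**Working it through.** **Inputs.** From Statistical Design and Power: t(17) = 3.19, p = 0.005, d = 0.34, f = 0.19, significance level 0.05 (taken as two-sided). From Study Design: 20 per arm, N = 40. Not stated: the pre-post correlation (rho) and the type of test behind t(17).

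**1. The plan's own figure.** For a two-group, two-session interaction, the noncentrality is lambda = f² x N x 2/(1 − rho), with df (1, 38). At f = 0.19 and rho = 0.65, lambda = 0.0361 x 80/0.35 = 8.25.

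| rho | power at f = 0.19 |
|---|---|
| 0.5 | 65% |
| 0.6 | 74% |
| 0.65 | 80% |
| 0.7 | 86% |
| 0.8 | 96% |

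So 80% can be reproduced, but only with an unstated rho of about 0.65.

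**2. What t(17) is.** As a pre-post test in 18 patients, t = 3.19 gives two-sided p = 0.0054, which matches the stated 0.005. As a two-group test in 19 patients, d would be at least 3.19 x √(1/9 + 1/10) = 1.47, which cannot be squared with 0.34. The pre-post reading is therefore used.

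**3. Size of the cited gain.** 3.19/√18 = 0.752 SD of change.

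**4. Power for that gain as a between-arm difference.** Let the 6 Hz arm exceed the 1 Hz arm by all of it. With 20 per arm the noncentrality of the t test on change is 0.752 x √(20/2) = 2.38 on 38 df, and power is 64.0% (63.9% with one df spent on age). On this scale rho does not enter.

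If the SD of change in this trial differs from that in the source study:

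| SD of change relative to source | power |
|---|---|
| 0.8 | 83% |
| 0.9 | 73% |
| 1.0 | 64% |
| 1.1 | 56% |
| 1.2 | 49% |

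**5. What 80% needs.** A between-arm difference of 0.909 SD of change. That is 0.909/0.752 = 1.21 times the cited gain. Equivalently, the SD of change would have to be about 17% smaller (0.752/0.909 = 0.827).

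**6. Linking f = 0.19 to the gain.** With equal SDs at both sessions, f = Delta/4, where Delta is the between-arm difference in change in raw SD. So f = 0.19 means Delta = 0.76. The SD of change is √(2(1 − rho)) raw SD. Then:
- f = 0.19 equals 0.752 SD of change at rho = 1 − (0.76/0.752)²/2 = 0.49, where power is about 64%.
- At rho = 0.65, f = 0.19 equals 0.76/√0.70 = 0.91 SD of change, which is the 80% case.

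No single rho makes f = 0.19 both equal to the cited gain and sufficient for 80% power.

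**7. Detectable difference at 80% power in raw SD.** 0.909 x √(2(1 − rho)) gives 0.91 at rho 0.5, 0.76 at 0.65, 0.57 at 0.8 and 0.41 at 0.90. The last value is illustrative. If d = 0.34 was standardised by the raw-score SD, which the plan does not say, then t and d together imply rho = 1 − (0.34/0.752)²/2 = 0.90.

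**The case against.** The strongest reply is that the power arithmetic is not wrong. At rho = 0.65, f = 0.19 gives 80% and f = 0.28 gives 98.5%, which also fits the figure of more than 95% stated for divided attention and theta power. One unstated correlation reconciles them all. That is true. The fault lies in the link between f = 0.19 and its cited source.

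Second, the 64% rests on 18 patients. The exact 95% confidence interval for 0.752 runs from about 0.22 to 1.27, which corresponds to power from about 10% to 97%. This stands: 64% is the value at the point estimate, and the cited data do not exclude 80%. But the plan says that its power was calculated from these data, and at the observed effect they do not return 80%.

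Third, the source test is inferred. Preliminary Studies gives p = 0.003 for the EVO study, while the power section gives p = 0.005. The cited papers, which may explain f, are not available here. This is a fair reason to ask for the derivation.

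Fourth, the plan words the gain as a hypothesis and the effect size as expected, admits that processing speed was not assessed with tACS, and gives a rationale for an added effect of stimulation. A first trial often has no prior estimate of its own contrast. All of that is fair, and assuming an effect would be acceptable. Presenting it as calculated from preliminary data is not.

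**Conclusion.** The concern holds. The SDMT power rests on a training gain that both arms can obtain, and the documents contain no 6 Hz versus 1 Hz estimate for SDMT. Even if the whole EVO-sized gain is credited to the difference between arms, power is about 64%, not 80%. A smaller increment gives less: half the gain (0.376 SD of change) gives 21%.

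The 64% assumes that t(17) is a pre-post test in 18 patients, that the SD of change here is similar to that study's and equal in both arms, and that all 40 participants contribute. It does not show that the true 6 Hz effect is small, since the documents do not estimate that effect. The point concerns SDMT only and takes no position on the divided attention power. It should be fixed.

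**What to change.** Three changes of wording:

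1. In Statistical Design and Power, under processing speed, show how f = 0.19 and the pre-post correlation were derived for the 6 Hz versus 1 Hz contrast. If they were not so derived, label f = 0.19 an assumption that does not come from tACS data on SDMT.
2. Replace the unconditional 80% with the detectable difference: about 0.91 SD of SDMT change at 80% power, two-sided 0.05, 20 per arm. In raw SD this is 0.76 if rho is 0.65 and 0.41 if rho is 0.90, with the source of any rho given. Add that an increment the size of the cited EVO gain would have about 64% power.
3. In Study Design and at the head of Statistical Design and Power, make the trial-level claim of more than 80% power conditional for SDMT.

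The cost is a protocol text edit and a less favourable stated power for SDMT. Nothing changes for patients, conduct or analysis.
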